## APPENDIX D. SAMPLE LIST OF EXCLUDED AND CAUTIONARY MEDICATIONS, WITH ADDITIONAL GUIDANCE NOTED

Excluded
Strong CYP3A inducers – avasimibe, carbamazepine, enzalutamine, mitotane, phenytoin, rifampin, St. John's wort
Cautionary, Additional Guidance Noted ^
Moderate CYP3A inducers – bosentan, efavirenz, etravirine, modafinil, nafcillin
Strong CYP3A inhibitors – boceprevir, clarithromycin, cobicistat, conivaptan, danoprevir/ritonavir, elvitegravir/ritonavir, idelalisib,* indinavir, itraconazole, ketoconazole, lopinavir/ritonavir, mibefradil, nefazodone, neflfinavir, paritaprevir/ritonavir combinations, posaconazole, ritonavir, saquinavir, telaprevir, telithromycin, tipranavir/ritonavir, voriconazole
Moderate CYP3A inhibitors – amprenavir, aprepitant, atazanavir, cimetidine, ciprofloxacin, clotrimazole, crizotinib,* cyclosporine,* darunavir/ritonavir, diltiazem, dronedarone, erythromycin, fluconazole, fluvoxamine, fosamprenavir, imatinib,* isavuconazole, tofisopam, verapamil
P-gp substrates – aliskiren, ambrisentan, colchicine, dabigatran etexilate, digoxin, everolimus,* fexofenadine, lapatinib,* loperamide, maraviroc, nilotinib,* ranolazine, saxagliptin, sirolimus,* sitagliptin, talinolol, tolvaptan, topotecan*
P-gp inhibitors – amiodarone, captopril, carvedilol, felodipine, quercetin, quinidine, ranolazine, ticagrelor
Cautionary
Warfarin and Coumarin Derivatives (e.g., phenprocoumon)**
BCRP substrates – methotrexate,* mitoxantrone,* irinotecan,* lapatinib,* rosuvastatin, sulfasalazine, topotecan*
OATP1B1/1B3 substrates – atrasentan, atorvastatin, ezetimibe, fluvastatin, glyburide, rosuvastatin, pitavastatin, pravastatin, repaglinide, simvastatin acid, telmisartan, valsartan, olmesartan
BCRP inhibitors – geftinib*

Note that this is not an exhaustive list. For an updated list, see the following link:

<https://www.fda.gov/Drugs/DevelopmentApprovalProcess/DevelopmentResources/DrugInteractionsLabeling/ucm080499.htm>

In addition to the medications listed in this table, subjects receiving venetoclax should not consume grapefruit, grapefruit products, Seville oranges (including marmalade containing Seville oranges) or Starfruits.

^ Avoid concomitant use with venetoclax. Alternative treatments should be considered. Refer to Protocol Section 5.3 and Section 5.4.

\* These are anticancer agents; consult contact the AbbVie medical monitor before use.

\*\* Closely monitor the international normalized ratio (INR).

## APPENDIX E. DEFINITIONS OF LABORATORY AND CLINICAL TUMOR LYSIS SYNDROME

Metabolic Abnormality	Criteria for Classification of Laboratory Tumor Lysis Syndrome	Criteria for Classification of Clinical Tumor Lysis Syndrome
Hyperuricemia	Uric acid > 8.0 mg/dL (475.8 $\mu$ mol/L) in adults	
Hyperphosphatemia	Phosphorus > 4.5 mg/dL (1.5 mmol/L) in adults	
Hyperkalemia	Potassium > 6.0 mmol/L	Cardiac dysrhythmia or sudden death probably or definitely caused by hyperkalemia
Hypocalcemia	Corrected calcium < 7.0 mg/dL (1.75 mmol/L) or ionized calcium < 1.12 mg/dL (0.3 mmol/L) a	Cardiac dysrhythmia, sudden death, seizure, neuromuscular irritability (tetany, paresthesias, muscle twitching, carpopedal spasm, Trousseau's sign, Chvostek's sign, laryngospasm, or bronchospasm), hypotension, or heart failure probably or definitely caused by hypocalcemia
Acute kidney injury b	Not applicable	Increase in the serum creatinine level of 0.3 mg/dL (26.5 $\mu$ mol/L) (or a single value > 1.5 $\times$ the upper limit of the age-appropriate normal range if no baseline creatinine measurement is available) or the presence of oliguria, defined as an average urine output < 0.5 mL/kg/hr for 6 hrs

a. The corrected calcium level in mg/dL = measured calcium level in mg/dL + 0.8  $\times$  (4-albumin in g/dL).

b. Acute kidney injury is defined as an increase in the creatinine level of at least 0.3 mg/dL (26.5  $\mu$ mol/L) or a period of oliguria lasting 6 hours or more. By definition, if acute kidney injury is present, the subject has clinical tumor lysis syndrome.

Note: In laboratory tumor lysis syndrome, 2 or more metabolic abnormalities must be present during the same 24-hour period within 3 days before the start of therapy or up to 7 afterward. Clinical tumor lysis syndrome requires the presence of laboratory tumor lysis syndrome plus an increased creatinine level, seizures, cardiac dysrhythmia, or death.

Source: Howard SC, Jones DP, Pui CH. The tumor lysis syndrome. N Engl J Med. 2011;364(19):1844-54.

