### Prophylaxis and Management of Tumor Lysis Syndrome

There is a potential risk for TLS in subjects with AML, especially in those with elevated leukocyte count, circulating blasts, elevated pretreatment LDH levels, dehydration, or renal dysfunction.

Venetoclax can cause rapid reduction in tumor and thus poses a risk for TLS. Changes in electrolytes consistent with TLS that require prompt management can occur as early as 6 to 8 hours following the first dose of treatment ([Appendix F](#)). Definitions of laboratory TLS and clinical TLS are provided in [Appendix E](#) (Howard grading classification). If a subject experiences blood chemistry changes suggestive of TLS, the dose of venetoclax may be withheld and/or reductions may be required.

Tumor lysis syndrome prophylaxis must be initiated in all subjects before the first dose of study drug or first new escalated dose. For subjects who had dose delay or interruptions TLS prophylactic measures may need to be implemented based on the disease status prior to resuming treatment. Below are the minimum requirements for TLS prophylaxis and management. Additional prophylaxis and monitoring procedures for TLS should be implemented as per institutional/regional standards.

- An oral agent to reduce the uric acid level (e.g., allopurinol) to be initiated at least 72 hours prior to dosing. Treatment may need to be continued for up to 28 days based on the ongoing risk of TLS development. Subjects allergic to or otherwise unable to receive allopurinol must use another uric acid reducer starting at least 72 hours prior to dosing or rasburicase on the day of treatment (prior to venetoclax dosing).
- Adequate hydration per day starting from at least 24 hours prior to first dose or any dose escalation.
- TLS Chemistry panel (creatinine, potassium, calcium, inorganic phosphorus, lactate dehydrogenase, and uric acid) will be performed real-time pre-dose, 4 - 6 hours post-dose and 24-hours post-dose for each venetoclax dose escalation, and as deemed necessary per investigator to monitor TLS.
- TLS Chemistry panel results (creatinine, potassium, calcium, inorganic phosphorus, lactate dehydrogenase, and uric acid) must be reviewed by the investigator in real time and prior to the subject's next dose to ensure appropriate subject management.

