- If any clinically significant laboratory changes are observed within the first 24 hours after initiation of dosing or after a dose escalation, see [Appendix F](#) for management guidelines. Refer to table in [Appendix E](#) for definitions of laboratory and clinical TLS.
- If subjects develop TLS and the treatment is withheld, they should be admitted and managed as inpatient until the ramp-up is complete and TLS labs have normalized.

Subjects with reduced renal function ( $\text{CLcr} < 80 \text{ mL/min}$ , Cockcroft-Gault formula) require more intensive prophylaxis and monitoring to reduce the risk of TLS when initiating treatment with venetoclax. For subjects with a higher risk for TLS and lower creatinine clearance, additional measures with more intensive lab monitoring and intervention should be implemented ([Appendix F](#)).

If a subject meets criteria for clinically significant laboratory or clinical TLS please follow institutional guidelines or recommendations in [Appendix G](#); no additional venetoclax dose should be administered until resolution.

For continued dosing of venetoclax, monitor for evidence of TLS during study treatment, and manage abnormalities of serum creatinine, and electrolytes promptly. After resolution of electrolyte imbalances ([Appendix F](#)), venetoclax may be continued at the original dose after discussion between the investigator and the AbbVie TA MD.

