Calcium $\leq$ 7.0 mg/dL (1.75 mmol/L) AND Subject symptomatic (e.g., muscle cramps, hypotension, tetany, cardiac arrhythmias)	
 
Administer calcium gluconate 50 to 100 mg/kg IV slowly with ECG monitoring.
 
Telemetry.
 
Recheck potassium, phosphorus, uric acid, calcium and creatinine in 1-hour STAT. 
 
If calcium normalized 1 hour later, repeat potassium, phosphorus, uric acid, calcium and creatinine 2 and 4 hours, later, if no other evidence of tumor lysis.
 
 
 
Calculate corrected calcium and check ionized calcium if albumin low.
 

Hyperphosphatemia	
Phosphorus $\geq$ 5.0 mg/dL (1.615 mmol/L) with $\geq$ 0.5 mg/dL (0.16 mmol/L) increase	
 
Administer a phosphate binder (e.g., aluminum hydroxide, calcium carbonate, sevelamer hydroxide, or lanthanum carbonate).
 
Nephrology (or other acute dialysis service) notification (dialysis required for phosphorus <math>\geq</math> 10 mg/dL).
 
Recheck potassium, phosphorus, uric acid, calcium and creatinine in 1-hour STAT. 
 
If phosphorus <math><</math> 5.0 mg/dL 1 hour later, repeat potassium, phosphorus, uric acid, calcium and creatinine 2 and 4 hours, later, if no other evidence of tumor lysis.
 
 
 

Creatinine	
Increase $\geq$ 25% from baseline	
 
Start or increase rate of IV fluids.
 
Recheck potassium, phosphorus, uric acid, calcium and creatinine in 1 to 2 hours STAT.
 

ECG = electrocardiogram; IV = intravenous; ULN = upper limit of normal; WNL = within normal limit

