10.3.2 Statistical Methods

For each lab test for which NCI criteria exist, shift tables will be generated that cross tabulate the number of subjects with baseline values of Grade 0, Grade 1, Grade 2, Grade 3, or Grade 4 versus maximum post-baseline of Grade 0, Grade 1, Grade 2, Grade 3, or Grade 4. All treated subjects will be included in the cross tabulation regardless whether baseline or post-baseline measurements are collected.

Separate laboratory shifts tables based on the two criteria below will be generated for each laboratory tests related to CTCAE:

- Shifts from Grade 0 (Normal) at baseline to Grade 1 - 4 Post-baseline (maximum) and worsening from an abnormal baseline value of at least one grade up post-baseline (maximum)
- Shifts from Grade 0 - 2 at baseline to Grade 3 or 4 Post-baseline (maximum) and from Grade 3 at baseline value to Grade 4 post-baseline (maximum).

The maximum NCI grade value is the value with highest NCI grade collected after the first dose of study drug and within 30 days following the last dose of study drug. In cases where multiple values are collected on the same day, the maximum grade value and minimum grade value will be selected as the value for that day for the post-baseline grade value and for the baseline grade value, respectively.

Detailed listings of data for subjects experiencing NCI CTCAE Grade 3 to 4 blood chemistry and hematology values will be provided. All measurements collected, regardless of the number of days after the last dose of study drug, will be included in these listings.

The number and percentage of subjects with liver Enzyme value meeting the criteria for potential drug-induced liver injury ($ALT > 3 \times ULN$ or $AST > 3 \times ULN$ and $TBILI > 2 \times ULN$ within 72 hours [3 days if time stamp is not collected] of each other) will be presented.

The number and percentage of subjects meeting the Howard criteria for TLS will be presented. The Howard Criteria for TLS is defined as two or more of the following treatment-emergent lab changes within a 24-hour period. The evaluation period for TLS is after 1st dose of study drug to 7 days from the 1st dose of study drug.

- uric acid $> 475.8 \text{ mcmol/l}$,
- potassium $> 6 \text{ mmol/l}$,
- inorganic phosphorus $> 1.5 \text{ mmol/l}$
- calcium $< 1.75 \text{ mmol/l}$.

11.0 Summary of Changes Between the Previous Version of SAP and the Current SAP

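### Appendix E's two calcium limits for laboratory TLS describe very different degrees of hypocalcemia, and the ionized limit would practically never be met

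*Protocol*

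**What the plan says.** The hypocalcemia row of protocol Appendix E gives two laboratory limits as alternatives: "Corrected calcium < 7.0 mg/dL (1.75 mmol/L") "or ionized calcium < 1.12 mg/dL (0.3 mmol/L"). Footnote a defines the albumin adjustment for the first: "The corrected calcium level in mg/dL = measured calcium level in mg/dL + 0.8" times (4 minus albumin in g/dL). The note under the table makes hypocalcemia one of the components of laboratory TLS, for which "2 or more metabolic abnormalities must be present during the same 24-hour period". Clinical TLS in turn requires laboratory TLS.

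Protocol Section 6.2 sends investigators to Appendix E "for definitions of laboratory and clinical TLS", and ties venetoclax administration to whether TLS criteria are met. The same section lists the scheduled monitoring: "TLS Chemistry panel (creatinine, potassium, calcium, inorganic phosphorus, lactate dehydrogenase, and uric acid"). Ionized calcium is not in that list, nor in the laboratory table of the Operations Manual (Table 1). The calcium row of Appendix F, which applies to symptomatic subjects with calcium at or below 7.0 mg/dL, does call for it: "Calculate corrected calcium and check ionized calcium if albumin low". It gives no ionized threshold.

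SAP Section 10.3.2 has its own laboratory count: "The Howard Criteria for TLS is defined as two or more of the following treatment-emergent lab changes within a 24-hour period". Its calcium item is a value below 1.75 mmol/L, with no ionized alternative and no statement of whether calcium is corrected for albumin. SAP Section 10.2.3 separately counts TLS reported as an adverse event, found by a MedDRA query.

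**The concern.** Two limits offered as alternatives for one abnormality should mark a broadly similar degree of it. Here one number is about a sixth of the other. If ionized calcium makes up a substantial part of total calcium, the second limit is far stricter than the first and does little work.

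The definition is operative. Investigators are directed to it to recognize TLS, and protocol actions on dosing follow from that. TLS events that they report enter the SAP's adverse event summary. The TLS rate is named in the secondary objectives (protocol Section 3.1), and safe outpatient initiation is the question the trial was set up to answer (Section 2.1).

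**Working it through.** **Inputs from the documents** (Appendix E): corrected limit 7.0 mg/dL (1.75 mmol/L); ionized limit 1.12 mg/dL (0.3 mmol/L); footnote a for the albumin correction. From SAP Section 10.3.2: calcium below 1.75 mmol/L.

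**Assumption:** the ionized share of total calcium, *f*. The documents do not give it. It is varied from 0.35 to 0.55.

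**Step 1. Reproduce the printed units.** The row's own conversion factor is 7.0 / 1.75 = 4.0. Then 1.12 / 4.0 = 0.28 mmol/L, printed as 0.3. With the atomic mass of calcium (40.078), 7.0 mg/dL is 1.747 mmol/L and 1.12 mg/dL is 0.279 mmol/L. Both conversions hold, so the row contains no conversion error.

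**Step 2. Compare the two limits.** 1.12 / 7.0 = 0.16, and on the printed mmol/L figures 0.3 / 1.75 = 0.17. The limits would match only if about one sixth of calcium were ionized.

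**Step 3. Size the gap.** Matching ionized level = 7.0 × *f*; factor = 7.0 × *f* / 1.12; on the rounded mmol/L figures, factor = 1.75 × *f* / 0.3. The total calcium at which the printed ionized limit would be reached is 1.12 / *f*.

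| Assumed *f* | Ionized level matching 7.0 mg/dL | Factor (mg/dL) | Factor (mmol/L) | Total calcium at printed ionized limit |
|---|---|---|---|---|
| 0.35 | 2.45 mg/dL (0.61 mmol/L) | 2.2 | 2.0 | 3.2 mg/dL |
| 0.40 | 2.80 mg/dL (0.70 mmol/L) | 2.5 | 2.3 | 2.8 mg/dL |
| 0.45 | 3.15 mg/dL (0.79 mmol/L) | 2.8 | 2.6 | 2.5 mg/dL |
| 0.50 | 3.50 mg/dL (0.88 mmol/L) | 3.1 | 2.9 | 2.2 mg/dL |
| 0.55 | 3.85 mg/dL (0.96 mmol/L) | 3.4 | 3.2 | 2.0 mg/dL |

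These figures test consistency. They are not proposed thresholds.

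**Step 4. A low-albumin illustration** (invented values). Take measured calcium 6.5 mg/dL and albumin 2.5 g/dL. Corrected calcium = 6.5 + 0.8 × (4 − 2.5) = 7.7 mg/dL, so the corrected limit is not met and only the ionized limit could count. To meet it, ionized calcium would have to be below 1.12 / 6.5 = 17% of the measured value, which is far below the assumed range.

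**Step 5. The same subject under the SAP.** Measured calcium is 6.5 / 4.0 = 1.63 mmol/L, below 1.75. Corrected calcium is 7.7 / 4.0 = 1.93 mmol/L, above 1.75. If the SAP means measured calcium, this subject meets its calcium item but not Appendix E's. If it means corrected calcium, the subject meets neither. The SAP does not say which.

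**The case against.** The strongest reply is that the plan contains no arithmetic error and little depends on this cell.

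- **The units agree, and the gap needs an outside figure.** Both points stand. No figure in the documents relates ionized to total calcium, and nothing says the two limits were meant to be equivalent. The factor is therefore conditional on the assumed share. It is still at least 2.0 across 35% to 55% in either unit, so the conclusion does not depend on the exact share.
- **The criterion is an either/or.** This stands. A reader might infer that Appendix E cannot detect hypocalcemia. It can, through corrected calcium below 7.0 mg/dL, and the Appendix F sentence that mentions ionized calcium asks for corrected calcium first.
- **Ionized calcium is rarely measured here.** This stands. It is not scheduled and would arise only as a conditional or discretionary test.
- **The SAP's laboratory count is untouched.** This stands. The ionized figure is not used there. It does not cover the adverse event count, which depends on what investigators report.
- **The table is attributed to a published classification.** Whether the entry was copied faithfully cannot be checked from these documents. A reader might infer that 1.12 is a mmol/L value with the wrong label. The documents do not show this. The printed 0.3 mmol/L is consistent with 1.12 mg/dL, and 1.12 mmol/L would be 1.12 × 4.0 = 4.48 mg/dL. That is 64% of 7.0, so it would not match the corrected limit at the assumed shares either.

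**Conclusion.** The point holds in a limited form. The two alternatives in Appendix E are far apart: the ionized limit is 16% to 17% of the corrected limit. At an assumed ionized share of 35% to 55%, it lies about 2.2 to 3.4 times below the matching level on the mg/dL figures, or 2.0 to 3.2 times on the rounded mmol/L figures. It would practically never be met, and it adds almost nothing in the low-albumin setting where Appendix F asks for the test.

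The exposure is limited to an investigator who classifies or reports TLS from an ionized result, and to the protocol actions that depend on that classification. It would be tempting to express this as one missed case in 60 subjects, or 1.7 percentage points. The documents do not support that figure: they give no rate of ionized testing, the program rate below 1% in Section 4.2 is for clinical TLS, and the SAP's laboratory count cannot lose a case this way. The expected effect on reported rates is small. The correction is still worth making, because this is a safety definition that sites apply in real time.

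**What to change.** Check the ionized-calcium value and unit in Appendix E against the cited classification. Then reconcile that entry with the corrected-calcium limit in the same cell, or state that the two are deliberately different and why. In SAP Section 10.3.2, state whether the 1.75 mmol/L criterion applies to measured or albumin-corrected calcium, so that investigators and the analysis work from one TLS definition. This review does not propose a threshold.

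The cost is one table cell in the protocol and one clarifying line in the SAP, with no new tests. If the SAP specifies corrected calcium, it also needs a rule for which albumin value to use. In the Operations Manual's Table 1, albumin is part of clinical chemistry but not of the TLS panel.

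### Appendix E classifies acute kidney injury without laboratory TLS in two opposite ways, so the same subject may be managed and reported differently across sites

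*Protocol*

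**What the plan says.** **Protocol, Appendix E.** Four metabolic abnormalities carry a laboratory threshold: uric acid, phosphorus, potassium and calcium. The acute kidney injury row is marked as not applicable in the laboratory column and has an entry only in the clinical column. Footnote b belongs to that row. It states "Acute kidney injury is defined as an increase in the creatinine level of at least 0.3 mg/dL", or oliguria for 6 hours or longer, and then: "By definition, if acute kidney injury is present, the subject has clinical tumor lysis syndrome".

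The Note below the table states "In laboratory tumor lysis syndrome, 2 or more metabolic abnormalities must be present during the same 24-hour period", inside a window running from 3 days before therapy to 7 days after its start. It continues: "Clinical tumor lysis syndrome requires the presence of laboratory tumor lysis syndrome plus an increased creatinine level, seizures, cardiac dysrhythmia, or death".

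**Protocol, Section 6.2.** "Definitions of laboratory TLS and clinical TLS are provided in" Appendix E. Two instructions then depend on the classification:
- "If a subject meets criteria for clinically significant laboratory or clinical TLS", sites are sent to institutional guidelines or Appendix G, and "no additional venetoclax dose should be administered until resolution".
- If a subject develops TLS and treatment is withheld, "they should be admitted and managed as inpatient until the ramp-up is complete" and the TLS laboratory values are back to normal.

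**Protocol, Appendix F.** A separate creatinine row covers a rise of 25% or more from baseline and calls for IV fluids and a repeat panel within 1 to 2 hours. It does not say whether such a rise is TLS.

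**SAP.** TLS is counted in two ways. Section 10.2.3 searches reported adverse events with the narrow SMQ, within 7 days of first dose. Section 10.3.2 counts subjects with two or more of four laboratory changes (uric acid, potassium, phosphorus, calcium) in 24 hours. Sections 10.2.1 and 10.2.2 tabulate adverse events leading to venetoclax interruption and those resulting in hospitalization. No clinical TLS tabulation is planned.

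**The concern.** One sentence makes acute kidney injury sufficient for clinical TLS. The other makes laboratory TLS necessary. Both cannot hold for a subject whose creatinine rises while fewer than two of the four metabolic abnormalities are present, and the appendix does not say which sentence governs.

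This is more than a wording matter, because Appendix E is the definition that Section 6.2 uses. Whether outpatient ramp-up is safe is part of the study's stated hypothesis, the TLS rate is named in a secondary objective, and TLS is an adverse event of special interest. Creatinine is on the TLS panel at every venetoclax escalation, and subjects may enter with creatinine clearance as low as 30 mL/min, so investigators can expect to meet the question. If one site reads the footnote and another the Note, the same laboratory result may lead to a different dosing decision, a different place of care and a different adverse event term.

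**Working it through.** The plan gives no figure for this point, so there is none to reproduce. The check applies each rule literally to the possible profiles.

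**Rules**
- Footnote b: acute kidney injury (AKI) implies clinical TLS. No further condition and no time window is stated.
- Note: clinical TLS implies laboratory TLS, plus raised creatinine, seizure, dysrhythmia or death.
- SAP Section 10.3.2: two or more of the four analytes in 24 hours, within 7 days of first dose.

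| Profile | Footnote b | Note | SAP laboratory count |
|---|---|---|---|
| AKI by creatinine, no metabolic abnormality | clinical TLS | not clinical TLS | no |
| AKI by creatinine, one abnormality | clinical TLS | not clinical TLS | no |
| AKI by creatinine, two abnormalities in the same 24 hours | clinical TLS | clinical TLS | yes |
| Two abnormalities, no AKI or other clinical feature | silent | laboratory TLS only | yes |

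The rules split in the first two rows and agree in the third. AKI cannot itself supply the Note's precondition, because the table excludes it from the laboratory criteria. The last column never depends on creatinine, so it is the same whichever rule is used.

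One smaller mismatch remains. The Note's list of features omits oliguria, which footnote b accepts as AKI. For laboratory TLS with oliguria but no creatinine rise, the two texts again differ if read literally. The agreement in row three is therefore limited to a creatinine rise.

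**Overlap with Appendix F.** For a baseline creatinine of b mg/dL, a 0.3 mg/dL rise is 0.3/b. This reaches 25% when b ≤ 0.3/0.25 = 1.2 mg/dL.
- At b = 1.2 or lower, the same isolated rise meets both footnote b and the Appendix F creatinine row.
- At b = 1.5, the rise is 0.3/1.5 = 20%. It meets footnote b but not the Appendix F row.

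**Route into the results**
- TLS adverse events (SAP 10.2.3): exposed, through what the investigator reports as TLS in the first 7 days.
- Interruptions (SAP 10.2.1) and hospitalizations (SAP 10.2.2): exposed, through differences in management.
- Laboratory Howard count (SAP 10.3.2): not exposed.

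**Scale.** One reclassified subject is 1/60 = 1.7 percentage points. The documents give no rate of AKI without laboratory TLS. Purely as an assumption, rates of 5%, 10% and 20% give 0.05 × 60 = 3, 0.10 × 60 = 6 and 0.20 × 60 = 12 subjects. These are ceilings, since they need every site to apply footnote b and to report each case as TLS.

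**The case against.** **A reconciling reading exists.** Footnote b hangs on a row with an entry only in the clinical column. It can be read as saying that AKI is enough as the clinical feature once the Note's laboratory condition is met. That reading is plausible, but the footnote carries no such condition, and each of about 20 sites would have to infer it.

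**Section 6.2 leaves room for judgement.** The hold is limited to clinically significant laboratory or clinical TLS and defers to institutional guidelines or Appendix G. Admission applies only if TLS develops and treatment is withheld. Chemistry changes suggestive of TLS only permit withholding. This stands: different handling across sites is possible, not certain.

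**An isolated creatinine rise already has its own instruction.** Appendix F covers it, and Section 6.2 requires the panel to be reviewed in real time before the next dose. This stands in part. It tells the site what to do next, but not whether the event is TLS, and its threshold is not footnote b's.

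**Stronger readings that the documents do not support:**
- A reader might infer that a planned clinical TLS rate is undermined. The SAP plans none.
- A reader might infer that a comparison with the program rate below 1% is lost. Protocol Section 4.2 gives that figure as background to dose selection, and neither document plans to compare against it.
- A reader might infer that every creatinine rise is ambiguous. With laboratory TLS present, the two rules agree on it.
- A reader might treat clinical TLS as the trial's main safety endpoint. TLS is named alongside neutropenia in a secondary objective and alongside cytopenias as an event of special interest; the primary endpoint is CR + CRi.
- A reader might conclude that the case report form lacks the needed items. The form is not among the documents.

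**Conclusion.** The contradiction is real and narrow. For acute kidney injury without laboratory TLS, Appendix E says both that the subject has clinical TLS and that the subject does not. It matters because Section 6.2 uses that appendix for dosing and admission instructions, and because reported TLS events, interruptions and hospitalizations can follow from the choice.

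Its size cannot be derived from the documents. It depends on how often AKI occurs without laboratory TLS and on how sites read the appendix, and neither is given. The conclusion that the two sentences conflict needs no assumption about frequency. The conclusion that results could be affected assumes only that at least one such subject occurs and that sites do not all read the appendix alike. The point is worth correcting because the correction is cheap. It does not call the primary analysis or the laboratory TLS count into question.

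**What to change.** Reconcile footnote b and the Note so that Appendix E states one rule for AKI without laboratory TLS, and make the Note's list of clinical features match the table's clinical column. Align the wording in Section 6.2 and the Appendix F creatinine row so that a site can tell from the text which instruction applies to an isolated creatinine rise. Which rule is adopted is a clinical decision for the sponsor; no view is taken here.

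In the SAP, state whether clinical TLS is tabulated and, if so, under which rule. The laboratory part and the creatinine part can be derived from the TLS panel already drawn before dosing, at 4 to 6 hours and at 24 hours for each escalation. The oliguria part cannot come from that panel and would rest on what the investigator records.

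The cost is one or two sentences in Appendix E, cross-reference edits in Section 6.2 and Appendix F, and one sentence in the SAP, with no new sampling. The downside is that the count of reported TLS events may change. If subjects have already been classified, the report should say which rule was in force when.
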